# 6.2 Epidural Electrical Stimulation (ES)

Study engineers, physical therapists, and research technicians perform the device programming and determine maximum stimulation parameters in real time. Device operators have been trained by industry partners (i.e., Abbott) on device manipulation during previous studies utilizing the same technology in SCI patients.

The surface area of each OCTRODE electrode is 0.1319 cm^2 based on manufacturer's specifications.

Based on literature, we conclude that stimulation that results in a charge density per pulse of no more than 30  $\mu$ C/cm^2, poses no safety concerns.

The charge density per pulse is defined by multiplying the stimulation current amplitude originating from an electrode by the pulse width of the stimulation pulse and dividing by the total electrode surface area.

The lower limit for current amplitude per electrode that will be applied in this study is 0.1 mA; The lower limit for the pulse width that will be applied in this study is 250  $\mu$ s. Therefore, if we applied the lower limit stimulation amplitude of 0.1 mA, the upper limit of pulse width that could be selected to stay below the current density per pulse threshold per pulse is 39570  $\mu$ s; since the manufacturing limit of the device is 1000  $\mu$ s, 1000  $\mu$ s will be selected as the pulse width upper limit for this study. Similarly, if a stimulation pulse width of the stated minimum of 250  $\mu$ s was selected, up to 15.8 mA could be applied to stay below the charge density per pulse threshold; therefore, 15.8 mA will be selected as the upper limit for current density in this study. No combination of parameters will be selected to drive the charge density per pulse over 30  $\mu$ C/cm^2 (S.F Cogan et al., 2016; Mccreery et al., 1990).

ES task-specific daily training will consist of lower extremity stretching, supine and side lying activities, seated trunk strengthening and balance activities, and locomotor training including task-specific stand and step training on a treadmill and over ground. Standing and stepping training activities may be performed with body weight support and trainer assistance as needed to ensure the safety of subjects.

Training sessions will begin upon completion of baseline testing. Subjects will participate in 3 days a week training regimen over 1 month with a goal of achieving at least 12 sessions. Activities include tasks specific to supine intentional leg movement training, balance training, stand and step (reciprocal flexion/extension) training. Heart rate will be recorded prior to, and after, each session, and at any time the intervention is paused due to a concern. Environments include thebody weight support treadmill (BWST) system to allow trainer-assisted stand and step activities as needed, custom standing frame, and a hi/lo mat for supine and seated activities. As the subjects progress their intentional motor ability with standing and stepping, BWS willbe removed, and assist will continue to be provided on an as needed basis. Any visit to the laboratory when ES is enabled will be considered a training session. Activities chosen for each session will be based on the subject's progression. At or near the conclusion of the training regimen, a Neurologist with a specialty in MS will conduct a clinical examination with stimulation turned on.

Over the course of rehabilitation sessions with ES, one additional x-ray may be performed to

visualize the location of implanted leads. This x-ray will be performed if stimulation-enabled motor activity is remarkably inconsistent from session to session, which might indicate migration of either ES lead.

#### 6.3 **Period of Follow-Up after ES**

After 1 month of ES and task-specific training, each subject will be asked to complete follow-up assessments.

#### **Outcome Measures** 6.4

The following outcome measures will be collected with tests occurring over an approximately one-week period of time for each time point. Photographic and video images will be recorded throughout the study but will not be shown to anyone outside the study team without the subject's written consent.

		Pre/ No Stim	Stimulation + Task-specific Training			Post/ Stim ON and OFF	
Outcomes	Specific Measure	wk 0	wk 1	wk 2	wk 3	wk 4	wk 4/5
	Primary						
Gait Analysis	EMG, Kinematics, Kinetics	Χ					X
Voluntary Movement	EMG, Kinematics	Χ	Χ			Χ	X
Spasticity	MAS, Pendulum Test	Χ					Χ
Secondary							
Functinal Mobility	TUG	Χ					X
MS Quality of Life Inventory	MSQLI	Χ					X

Aim 1 will quantify the effect of ES and task-specific training on lower extremity motor function in individuals with severe lower extremity motor disability due to progressive MS using the primary outcomes of kinematics (movement), kinetics (forces), and electromyography (muscle activity, EMG) collected during gait, standing, and side lying motor tasks. Data will be reduced and summarized using standard biomechanical approaches, to quantify gait rhythm, lower extremity joint and body center of mass ranges of motion (during gait, standing, and side lying), and timing of muscle activations and ground reaction force peaks. Secondary outcomes include functional mobility assessments utilizing motion capture data, as well as the Timed Up and Go (TUG) test. Safety and tolerability will be assessed while monitoring vital signs and stimulation responsiveness during daily sessions and testing dates.

Aim 2 will determine the impact of ES and task-specific training on non-motor spinal related dysfunction in individuals with severe lower extremity motor disability due to progressive MS using the primary outcomes of the qualitative pendulum test (Smith et al., 2000) and the Modified Ashworth Scale to describe spasticity levels. Secondary outcomes will include the MS Quality of Life inventory that includes questions about bowel, bladder and sexual function, quality of life and pain, among others.

Aim 3 will be an *exploratory aim* to collect electrophysiological and biomarker data that may help us gain a mechanistic understanding of findings in Aims 1 and 2. To assess the Page 20 of 33 [name].

functional states of **spinal connectivity**, we will deliver transcutaneous electrical stimulation via pulses of 1 ms duration at intensities of up to 100 mA using biphasic, charge balanced stimulation (DS8R, Digitimer Ltd., UK). Stimulation will be delivered to the skin over the intra-spinous space between the spinous processes of the T10, T11, T12, L1, L2vertebrae, with subjects in a supine position. Evoked

potentials will be recorded via surface EMG electrodes placed bilaterally over the rectus femoris, vastus lateralis, medial hamstring, tibialis anterior, medial gastrocnemius, and soleus muscles. We will record evoked potentials while relaxed using stimulus intensities from 1-100 mA at increments of 10 mA for each stimulus locationT10-L2. Stimulus intensities that are at the threshold for evoking motor potentials will be delivered during the following actions: while attempting prolonged maximal contractions of all muscles; during attempts to contract the left leg; and during attempts to contract the right leg.

*Gait analysis:* Full body kinematic parameters will be acquired with a computerized video motion analysis system. A surface electromyography (EMG) system will be used for data collection. Muscle activity will be collected from all or a subset of the following lower extremity and trunk muscles: soleus, gastrocnemius, tibialis anterior, hamstrings, quadriceps, hip adductors, gluteus maximus, gluteus medius, abdominals and spinal extensors. Ground reaction force data will be acquired from force plates or pressure mat technology located in the floor or as in-shoe sensors. EMG and ground reaction force data will be time-synchronized with the motion cameras.

*Voluntary movement in side-lying and supine postures:* Voluntary movement data will be acquired during a variety of volitional tasks including standing, and supine and side-lying stepping movements. Kinematics and EMG measurements will be obtained from a motion analysis system and surface EMG system. All or a subset of the following muscles or muscle groups will be tested: soleus, gastrocnemius, tibialis anterior, hamstrings, quadriceps, hip adductors, gluteus maximus, gluteus medius, abdominals and spinal extensors.

*Spasticity:* One or both of the following will be used to measure lower extremity spasticity: the Modified Ashworth Scale (MAS) (Bohannon et al., 1987) where the subject will be placed in a supine position and flexor and extensor muscles are assessed according to the MAS protocol; and the pendulum test which is a biomechanical method of evaluating muscle tone using surface-based kinematic assessments that uses gravity to provoke muscle stretch reflexes during passive swinging of the lower limb.

*Functional mobility test:* The following test will be performed: Timed Up and Go (TUG) (Podsiadlo et al., 1991). The TUG test is used to assess a person's mobility and requires both static and dynamic balance.

*MS QOL Inventory (MSQLI):* Multiple Sclerosis Quality of Life Inventory (Fischer et al., 1999), a comprehensive outcomes assessment battery will be administered to assess many facets of the participants' quality of life. Several scores, are captured, including Overall Health Status, Modified Fatigue Scale, Sexual Satisfaction Scale, Bladder Control Scale, Bowel Control Scale, Perceived Deficits Questionnaire and Mental Health Inventory.

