- The proposed research is a pilot study which will explore epidural spinal stimulation (ES) in combination with task-specific training to improve lower limb function in 10 participants with Progressive MS.
- We will temporarily implant percutaneous ES leads through the skin overlying the lumbosacral enlargement and remove the leads following the 4-week study.
- Participants will serve as their own control via a comparison of pre- and poststimulation outcomes and outcome metrics captured during ES and when ES is off.
- Safety will be continuously evaluated during the 4-week stimulation and task specific training period, and during a post lead removal neurologist visit.
- The percutaneous leads are currently used clinically and are approved for patients with low back pain; use in participants with MS will be possible under an FDA IDE.

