# 3 Study Design

# 3.1 General Design

This is a pilot study that will include a total of 10 subjects with Progressive MS (EDSS 6.5). All subjects will complete 1 month of ES and task-specific training. Expected duration of subject participation is less than 2 months. Baseline assessments will be obtained prior to implantation and post-stimulation assessments will be obtained prior to explantation, with stimulation on and off.

SCREENING	BASELINE	STIMULATION	POST- STIMULATION	
	Baseline Assessments	Minimum 12 Sessions	End Assessments	
Assessment of Inclusion/Exclusion criteria by study team	Clinical, Electromyography, Movement Assessments& Surveys	Stimulation + Task- Specific Training	Clinical, Electromyography, Movement Assessments & Surveys	STUDY END
	No Stim	Percutaneous Stimulation	Stim on/Stim off	
l-month pre- enrollment	Week 0-1	Weeks 1-4	Week 4-5	

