# 3.2 Primary Study Endpoints

Due to the pilot phase design of this clinical trial, it is not feasible to designate primary study endpoints. With this in mind, we do consider the voluntary movement assessments, gait analysis, and functional mobility tests to be the primary sets of endpoints used to quantify ES-related datasets associated with addressing the specific aims of this proposal.

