# 5.3 Preparation and Administration/Implantation of Investigational Device

[figure not shown]
Description of ES system implantation/administration

We recently published a detailed explanation of the procedure to implant a permanent

electrode array connected to an implanted pulse generator, along with a detailed description of the electrophysiological approach used to guide electrode positioning over the lumbosacral enlargement in humans with SCI (Calvert, 2018). The same approach will be used during this study to guide electrode placement via electrophysiological monitoring of spinal motor evoked potentials.

The procedures for percutaneously implanting Abbott ES electrodes are performed daily at Mayo Clinic to treat patients suffering from neuropathic pain. Prior to implantation, subjects will undergo a pre-operative evaluation to minimize the risk of unexpected complications. Pre-operative assessments may be performed to check for any signs of infection.

To implant the temporary spinal electrodes, under fluoroscopy an electrode insertion needle will be placed into the epidural space using a paramedian approach and loss of resistance technique to advance through the ligamentum flavum, followed by fluoroscopic visualization of the needle's position. Once positioning is confirmed, the needle stylet will be removed, and the needle will be advancedinto the epidural space.

Then, the leads are advanced in an anterograde fashion to the level of the lumbosacral enlargement utilizing fluoroscopic guidance. Following electrophysiologic confirmation of electrode positioning, the needle and stylet will be removed, the implantation site will be dressed, and the leads will be secured to the skin via an adhesive bandage. The implantation site will be monitored for signs of infection, tissue erosion, or dislodged lead wires. One day post implantation, the first follow up will take place to evaluate for adverse events. Trained

Page 16 of 33 [name]. team members will monitor the percutaneous site on an ongoing basis during training session to ensure the site remains intact and sterile. Study team members have received training from a registered nurse within the pain specialty program at Mayo Clinic.

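### Stim-ON voluntary-movement EMG and lying-posture movement have no relaxed ES-on reference and no artefact rule, so pulse-evoked activity cannot be told apart from voluntary activation

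*Combined protocol and SAP*

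**What the plan says.** **Status of the outcome.** Section 3.2 declines to designate formal primary endpoints but adds "we do consider the voluntary movement assessments, gait analysis, and functional mobility tests to be the primary sets of endpoints". The outcome tables in 3.2 and 6.4 list voluntary movement (EMG, kinematics) and gait (EMG, kinematics, kinetics) as primary.

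**How it is recorded.** Section 6.4: "Voluntary movement data will be acquired during a variety of volitional tasks including standing, and supine and side-lying stepping movements". It continues: "Kinematics and EMG measurements will be obtained from a motion analysis system and surface EMG system". For Aim 1 the data are reduced to gait rhythm, ranges of motion, and "timing of muscle activations and ground reaction force peaks", by methods described only as customary in biomechanics.

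**When, and in which ES state.** Baseline is without stimulation. At the end, per section 3.1, "post-stimulation assessments will be obtained prior to explantation, with stimulation on and off". The schedule also places voluntary movement at weeks 1 and 4, under the stimulation-and-training columns.

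**The control.** Section 1 has participants act as their own control, through pre/post comparison and "outcome metrics captured during ES and when ES is off".

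**What the pulses can do.** Section 5.3 will "guide electrode placement via electrophysiological monitoring of spinal motor evoked potentials".

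**The one relaxed stimulated recording.** In exploratory Aim 3 (6.4): "We will record evoked potentials while relaxed using stimulus intensities from 1-100 mA at increments of 10 mA". Those pulses are transcutaneous, given at T10 to L2 with the participant supine.

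**The concern.** Lead placement relies on pulses at this site evoking muscle responses, so the protocol itself accepts that epidural stimulation can produce leg EMG without effort. If the settings used during the tasks do so too, an ES-on recording made during an attempt holds both the participant's own activation and the response to the pulses, with electrical artefact added to the EMG. Only the first matches the name of the outcome and the aim, set out in the background (1.1), of enabling volitional movement.

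The estimates are meant to feed later work. Section 7.2 uses them to size future studies, and 1.4.1 hopes to learn who may suit a permanent implant. An ON-OFF difference that cannot be apportioned between voluntary drive and direct stimulation serves those uses poorly. The leads come out after one month (1.5), so a recording that was not made cannot be recovered.

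**Working it through.** The plan gives no figure for this point. The check is which conditions are recorded, and what the contrasts can identify.

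**1. Conditions recorded for voluntary-movement EMG and kinematics**

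| | Relaxed | Attempting the task |
|---|---|---|
| ES off | not planned | baseline; post Stim-OFF |
| Epidural ES on | **not planned** | post Stim-ON; weeks 1 and 4 if ES is on at those readings |

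**2. What each contrast contains.** As a simplification, treat a recording as a sum of *V* (voluntary activity), *E* (pulse-evoked activity) and *A* (stimulus artefact, EMG only).

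- Post OFF − baseline = V(post, off) − V(base). No pulses are running, so *E* and *A* are absent.
- ON-attempt − OFF-attempt = [V(on) − V(off)] + E(attempt) + A.
- ON-attempt − baseline = [V(on) − V(base)] + E(attempt) + A.

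In the last two lines one observed difference holds three unknown parts. The analyses in 7.2 (post value regressed on baseline; ON and OFF correlations) and the repeated-measures ANOVA in the Study Summary work on the same recordings and cannot split them. Activation timing is not additive, but the difficulty is the same: an onset detected in a mixed signal may belong to either source.

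**3. What a relaxed ES-on recording adds.** ON-relaxed = E(relaxed) + A. At the same settings and posture, and with the same artefact:

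- ON-attempt − ON-relaxed = V(on) + [E(attempt) − E(relaxed)].

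The artefact cancels and the evoked part is reduced to its change with effort. If effort alters the evoked response, a remainder is left, so the difference is a reference and not an exact measure of *V*.

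**4. Do the stimulation limits rule evoked activity out?** The charge limit in 6.2 reproduces:

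- 30 µC/cm² × 0.1319 cm² = 3.957 µC per pulse.
- 3.957 µC ÷ 0.1 mA = 39,570 µs, as stated.
- 3.957 µC ÷ 250 µs = 15.8 mA, as stated.

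This is a tissue-safety bound. It says nothing about motor threshold, and 6.2 has staff determine parameters in real time. Whether task settings evoke responses is therefore open. No frequency is given, so the share of a record that pulses would occupy cannot be computed.

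**5. Does another recording fill the gap?**

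- Aim 3 pairs relaxed with attempted recordings, which is the right structure, but its pulses are transcutaneous and not the epidural ones used in the tasks.
- The Modified Ashworth Scale and pendulum test are passive. They are spasticity measures under a one-or-both rule, with no EMG specified and no match to the voluntary tasks.
- The stated data reduction names no blanking, artefact removal or separation of evoked responses.

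**The case against.** The case on the other side is substantial, and most of it limits the point without removing it.

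- **The objective is broader than voluntary drive.** Section 2.1 and Aim 1 concern motor function. For that question a direct contribution from stimulation may be part of the ES effect. This stands.
- **A clean contrast exists.** Baseline versus post Stim-OFF has no concurrent pulses. This stands.
- **Only part of the primary data is exposed.** Among the Aim 1 summaries, only activation timing is EMG-derived; EMG amplitude is not listed. Gait kinematics and kinetics describe function however it was produced. This stands, although movement in the lying postures can itself be evoked.
- **This is a ten-person, unblinded, single-arm pilot** with no power calculation. That lowers the severity. It does not excuse a gap that is cheap to close and cannot be closed afterwards.

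A reader might also draw stronger conclusions that the documents do not support:

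- *That the plan counts evoked activity as voluntary.* It never says how ON-state EMG will be interpreted. That reading comes only from the outcome's name and the absence of a separation step.
- *That the bias favours ES.* A change in timing has no favourable sign, and 1.4.2 lists both increased and decreased spasticity as possible under ES.
- *That task settings certainly evoke responses.* Section 5.3 concerns lead placement, not the settings used in the tasks.
- *That a percentage of each record is contaminated.* Any such figure would rest entirely on an assumed frequency and an assumed response duration.

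**Conclusion.** The point holds for Stim-ON EMG and for Stim-ON supine and side-lying movement. As planned, the ON-OFF and ON-baseline contrasts cannot separate voluntary activation from whatever the pulses evoke or add as artefact. Size and direction are unknown. The conclusion needs only that evoked activity is possible at the settings used; the documents show that it is possible at this site and nothing in them excludes it during the tasks. It does not extend to baseline versus post Stim-OFF, nor does it invalidate ON-OFF comparisons of gait function for the motor-function objective. It should be fixed, but it does not undermine the study as a whole.

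**What to change.** Amend section 6.4 as follows.

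1. At each ES-on voluntary-movement test, add a relaxed recording of about 30 seconds at the same settings, in the supine and side-lying postures. Do not attempt it in standing or gait, where a no-effort trial in the same posture is not achievable.
2. State an artefact-removal rule, applied before activation timing is computed. Drop a channel from ON comparisons if its artefact cannot be removed.
3. Report ON-attempt alongside ON-relaxed. Describe their difference as a reference for evoked activity and not as an exact measure of voluntary drive, because effort may change the evoked response.
4. Base any claim about voluntary function on baseline versus post Stim-OFF together with ON-attempt versus ON-relaxed. For gait and standing, let kinematics and kinetics carry the ON-OFF comparison, with ON-state EMG timing as supportive.

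**Cost.** Two postures × 30 s is about 1 minute of recording per test. If ES is on at weeks 1, 4 and 4/5, that is 3 × 1 = 3 minutes per participant. Set-up brings it to a few minutes per test, with sensors already worn. Signal processing is extra, and some EMG channels may be lost. Neither the sample size nor the stimulation settings change.

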# 7 Statistical Plan

# 7.1 Sample Size Determination

Due to the pilot phase of this study, no formal power calculations were performed for this proposal. The number of subjects was selected based on budgetary, space, and personnel time constraints. Ten participants (five males; five female) will be enrolled to complete this study, depending on need for contingency subjects. Participants will receive 4 weeks of ES and serve as their own control.

# 7.2 Statistical Methods

*Statistical Methods:* Continuous data will be summarized as median (inner quartile range). Categorical data will be presented as frequency (percentage). Graphical presentations of subject-level data will be used for all endpoints. Individual data points will be plotted over time, from pre to post stimulation and training.

*Modeling:* Statistical models will be used both to estimate the ES effect on endpoints, as well as to provide estimates of variability to enable sample size estimation for future studies. Models for post-ES treatment will be fit using linear regression using the baseline measure as a covariate. Both the ES treatment effect and the residual variance estimate will be reported. Standard deviations of the differences in pre- and post-ES measurements will also be reported. Furthermore, correlations between pre- and post-ES assessments, as well as post task specific training stim-off and stim-on assessments will be calculated to aid future study design. Transformations of endpoints to achieve symmetry in the distribution (normality will be difficult to assess with this sample size) will be used as necessary.

*Handling of Missing Data:* Due to the small sample size, sophisticated missing data techniques like imputation are likely to be unreliable. For all analyses, only subjects with complete data for the necessary analysis will be included. We will attempt to limit missing data by only enrolling participants who have the physical capacity to complete the training sessions. Only prospective enrollees who have been fully optimized from a rehabilitation point of view will be offered enrollment in the study. To minimize the financial burden on study participants and their families, they will be offered money to offset the cost of travel and accommodation during the study. If a study participant ends the study early, a similar replacement participant will be sought. Missing data in survey instruments will be minimized by allocating time during the study for survey completion, and inspection for completion by study coordinators before moving to the next component of the study.

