enabled: 1) intentional control of motor activity and leg movement; 2) standing; 3) intentional control of step-like movements while side lying with legs suspended in a gravity neutral position, and 4) intentional control of bilateral leg flexion and extension while upright with body weight supported by a harness. More recently, we reported that the same participant achieved independent standing, stepping on a treadmill while using arm support bars to maintain balance, and posture and over ground walking with minimal assistance (M. L. Gill et al., 2018). To date, the second participant demonstrated similar ES-enabled motor achievements. In addition to reports of ES enabling lower extremity motor functions, improvements in upper extremity(Lu et al., 2016), cardiovascular (Aslan et al., 2018; S. J. Harkema, Legg Ditterline, et al., 2018; S. J. Harkema, Wang, et al., 2018; Herrity et al., 2018; West et al., 2018), and urologic functions (Herrity et al., 2018) have been reported in participants with SCI.

Prior to proposing a trial to assess the use of permanently implanted epidural spinal stimulation in participants with progressive MS, it is pertinent to assess whether these individuals are responsive to stimulation using a temporary percutaneous lead used commonly in clinical practice for low back pain and in research for participants with spinal cord injury.

[figure not shown]

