# Steps taken to minimize the occurrence and severity of associated risks:

Trained study staff and medical technicians will directly oversee all tasks. Body weight support, a safety gait belt, and other safety measures as necessary will be utilized to lessen the risks involved with rehabilitation and weight-bearing tasks. To mitigate risks in general, the protocol will be conducted as stated, medical professionals will be consulted, and care will be provided to address any study-related concerns that arise. All members of the research team will be trained to identify the occurrence of risks related to this study. If risk occurrence is observed, study-related activities will be halted until appropriate medical care

is given and it is deemed safe for the subject to continue study-related activities. Because the interventions have been used for individuals with subjects with spinal cord injury and subjects will have been carefully screened, we do not anticipate any serious adverse events in this study. However, if they do occur, serious adverse events will be reported to the PI, medical monitor, IRB and FDA within the appropriate reporting timeframes. Adverse events will be reported to the PI, the site medical monitors IRB, and FDA within the appropriate reporting timeframes.

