# 3.3 Primary Safety Endpoints

Primary safety endpoints of the study will be oriented to adverse events that could originate from the implantation of the ES electrodes, or the operation of the neurostimulator device as well as to those that could arise from performing the task-specific training sessions. Participants will be asked to report any discomfort that they encounter throughout the study. A detailed selection of the candidates by the Principal Investigators and the study team will be crucial to select individuals who fit the inclusion criteria of the study, minimizing risk for

34-36

potential adverse events throughout the study. Subjects will undergo a screening phase oriented to identify conditions that could potentially represent a higher than the expected risk for conducting this study.

To visualize electrode positioning of the ES device, X-ray imaging will be performed. To limit adverse events that could result from operating the device, stimulation parameters will be selected within safe ranges as provided by the manufacturer.

#### Subject Selection, Enrollment and Withdrawal 4 Year 1 Year 2 Year 3 Month 1-3 4-6 7-9 10-12 16-18 19-21 13-15 22-24 25-27 28-30 31-33 Subject 1 Screening and baseline visit Subject 2 Stim + task-specific training, Subject 3 post-visit Subject 4 Subject 5 Subject 6 Subject 7 Subject 8 Subject 9 Subject 10

Data Analysis, Interpretation, Documentation

Ten subjects with a diagnosis of Progressive MS (EDSS 6.5) will be enrolled. Subjects will be selected based on the following criteria:

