# 7.3 Subject Population(s) for Analysis

All-completed population: Only subjects who completed all study related procedures and follow-up will be included; however, the PI may adjust this to include a subject who completed most of the study visits and procedures.

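### The safety endpoints have only a count-and-percentage rule and no all-implanted denominator; 0 of 10 would still be compatible with a true rate of up to 30.8%

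*Combined protocol and SAP*

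**What the plan says.** Section 3.3 introduces the endpoints as follows: "Primary safety endpoints of the study will be oriented to adverse events that could originate from the implantation of the ES electrodes". It adds events from operating the neurostimulator and from the training sessions. It gives no list of event types, no acceptable rate and no method of summary.

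Section 7.2 supplies the only numerical summary that suits a yes/no event: "Categorical data will be presented as frequency (percentage". It also promises subject-level graphs for all endpoints. The other quantities in 7.2 are a regression on baseline with its residual variance, standard deviations of pre/post differences, and correlations. All of these need paired measurements and cannot apply to adverse events. No interval for a proportion appears in sections 3.3, 7 or 8.

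On the expected result, section 1.4.2 states "we do not anticipate any serious adverse events in this study".

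Three statements bear on the denominator:
- Section 7.1: "Ten participants (five males; five female) will be enrolled to complete this study, depending on need for contingency subjects".
- Section 7.2: "If a study participant ends the study early, a similar replacement participant will be sought".
- Section 7.3: "Only subjects who completed all study related procedures and follow-up will be included". The PI may relax this for someone who completed most of the study. No separate safety population is named.

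**The concern.** If the trial goes as the protocol expects, the serious-event line will read 0 (0%). That display does not say which rates ten implants can exclude. It looks the same whether the true rate is very low or high enough to matter for an invasive procedure whose listed risks in section 1.4.2 include epidural hemorrhage, cord compression and paralysis.

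The denominator adds to this. Section 4.4.1 lists a study-related serious event among the reasons for withdrawal. A participant withdrawn for that reason could be replaced and fall outside the completers population. A percentage taken on completers could then omit the very event it is meant to count.

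What is at stake is how much the trial can claim about safety in this population. The efficacy results are not affected.

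**Working it through.** The plan states no safety rate, confidence level or interval, and its sample size rests on resources, so there is no figure of its own to reproduce.

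**Inputs**
- Participants: 10 (section 7.1 and the Study Summary).
- Expected serious events: 0 (section 1.4.2).
- Confidence level: two-sided 95%, an assumption.

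**Step 1: exact limit for zero events.** The Clopper-Pearson upper limit for 0 of n is 1 − 0.025^(1/n). For n = 10 this is 1 − 0.025^(0.1) = 1 − 0.6915 = 0.3085, or 30.8%. Check: 0.6915^10 = 0.025.

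**Step 2: how often zero would be seen.** P(0 of 10) = (1 − p)^10.
- True rate 5%: 0.95^10 = 0.60.
- True rate 10%: 0.90^10 = 0.35.
- True rate 20%: 0.80^10 = 0.11.

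A true rate of 10% would therefore give no events in about one such trial in three.

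**Step 3: sensitivity to the number implanted.** The same formula gives:

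| n implanted | Upper limit for 0 of n |
|---|---|
| 8 | 36.9% |
| 9 | 33.6% |
| 10 | 30.8% |
| 11 | 28.5% |
| 12 | 26.5% |

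**Step 4: sensitivity to the method.** For 0 of 10, the Wilson two-sided limit is 3.84/(10 + 3.84) = 27.8%, and the rule of three gives 3/10 = 30%. A one-sided 95% exact limit is 1 − 0.05^(0.1) = 25.9%. The message is the same under each, but a report should use one convention only.

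**Step 5: why the denominator matters (illustration).** Suppose 11 participants are implanted, one is withdrawn after a serious event and replaced, and ten complete.
- Completers: 0/10 = 0%, interval 0 to 30.8%.
- All implanted: 1/11 = 9.1%, interval 0.2% to 41.3%.

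An exact interval on the wrong population would look rigorous and still leave out the event.

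**The case against.** This is an openly descriptive pilot in which "no formal power calculations were performed for this proposal". Safety is not a formal objective: sections 2.1 and 2.2 concern motor function, spasticity and non-motor dysfunction. Safety is followed event by event, which suits ten participants. All events are recorded and followed (8.2), each is reviewed for causality and seriousness (8.2), one related serious event can suspend the study (8.4), and there is an independent medical monitor (10.1). A count out of ten also shows its own denominator, and any reader can work out the interval. All of this stands, and it is why the point is an improvement rather than an error. None of it supplies a statement of what the data can exclude.

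A reader might infer more than the documents support:
- **That the trial would declare the device safe on 0%.** No section says so, and no safety success criterion is set. Section 1.4.2 says only that serious events are not anticipated.
- **That this pilot is the safety gate to permanent implants.** The sentence in section 1.1 beginning "Prior to proposing a trial to assess the use of permanently implanted epidural spinal stimulation" goes on to give responsiveness to stimulation as the question to settle first.
- **That a percentage is the sole presentation planned.** Section 7.2 also promises subject-level graphs. Applying its categorical rule to adverse events is an inference, though if it fails, the safety endpoints have no numerical summary at all.
- **That infection, lead migration or early lead removal are designated primary safety endpoints.** Section 3.3 does not list them as such.

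One technical caveat also stands. The interval treats N as fixed, while section 8.4 can halt enrollment after a related serious event. With no serious event that trigger is not met, so the 0/10 figure is unaffected. With one or more such events the interval is approximate.

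**Conclusion.** The point holds as a low-cost reporting improvement. The primary safety endpoints have no planned measure of precision and no denominator that guarantees every implanted participant is counted. The serious-event result the protocol expects, 0 of 10, would be compatible with a true rate of up to 30.8%. For 8 to 12 implanted, the corresponding limit runs from 36.9% down to 26.5%.

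This rests on three assumptions: a two-sided 95% level, the section 7.2 categorical rule being the one meant for adverse events, and independent participants with a common event rate. It does not show a contradiction in the plan, and it does not call for a larger sample.

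**What to change.** Add to section 7.2: the adverse-event endpoints of section 3.3 (serious events, and events related to implantation, device operation or training) will be reported as n/N (%) with an exact Clopper-Pearson two-sided 95% interval. N will be all participants in whom lead implantation was performed, including those later withdrawn or replaced. Add the same definition to section 7.3 as a safety population beside the completers population.

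Use this one convention in tables and text, and word any safety conclusion in terms of the upper limit. For 0 of 10, the statement would be that the interval extends to 30.8%.

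The cost is a few sentences and one table column, with no new data, visits or procedures. The downside is a less favourable-looking safety statement.
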